16.8.7 Analysis of the Secondary Endpoints

Analyses of continuous data based on diary data will use a similar model to the primary analysis, and continuous scale endpoints will be analysed by the same MMRM methodology as for HIT-6. Response variables will use similar analyses as the key secondary response

endpoints. The endpoints; patients with a migraine on the day after first dosing and 100% responders for MMDs and MHDs (Weeks 1-12) will be analysed using an extended Cochran-Mantel-Haenszel (CMH) test, adjusting for the stratification factor (MHDs at baseline: $\leq 14 />14$).

16.8.8 Analysis of the Exploratory Endpoints

Analyses of continuous data based on diary data will use a similar model to the primary analysis, and continuous scale endpoints will be analysed by the same MMRM methodology as for HIT-6. Response variables will use similar analyses as the key secondary response endpoints.

16.8.9 Analysis of Subgroups

Details of subgroup analyses will be specified in the SAP.

16.9 Safety Analyses

16.9.1 Analysis of Adverse Events

Adverse events will be classified according to the time of onset of the adverse event:

- *pre-treatment adverse event* an adverse event that starts on or after the date the patient signed the *Informed Consent Form* and prior to the date and time of first infusion of IMP
- *treatment-emergent adverse event* (TEAE) an adverse event that starts or increases in intensity during or after administration of the first dose of IMP. Adverse events, sorted by system organ class (SOC) and preferred term, will be summarized.

Allocation of TEAEs to Study Periods

TEAEs will be allocated to study periods (these will be defined in the *Statistical Analysis Plan*).

16.9.2 Analysis of Other Safety Endpoints

The clinical safety laboratory test values, vital signs, and ECG parameter values will be summarized. Potentially clinically significant (PCS) values will be flagged and summarized.

Non-suicidal self-injury behaviour (considered separately) and no suicidal ideation or behaviour or the worst suicidal ideation or behaviour will be summarised for the double-blind treatment Period and the extension Period.

16.10 Sample Size and Power

The two prior eptinezumab Phase III studies, PROMISE-1 performed in an EM population and PROMISE-2 performed in a CM population, had the following effect sizes for the primary endpoint when compared to placebo (standard deviations):

- EM: 100 mg 0.69 (3.1), 300 mg 1.11 (3.1)
- CM: 100 mg 2.03 (5.8), 300 mg 2.60 (5.8)

The power was determined by simulating the testing strategy (10000 simulations) assuming normal distributions with similar mean and SD for continuous endpoints and similar success rates as the response variables in the Phase III studies for the corresponding population (EM or CM) without assuming the variables to be correlated. With 280 patients per treatment group, assuming that 40% of the patients will be from the EM population and 60% from the CM population, and that 2% of the patients do not have a post-baseline assessment of the primary endpoint, simulations show that the power for the test of the primary endpoint is approximately 94% for the comparison of 100 mg to placebo and 99% power for the comparison of 300 mg to placebo. The individual key secondary endpoints had a power of at least 68% for showing an effect, with a combined power of 58% for seeing an effect for all primary and key secondary endpoints and both doses in the testing strategy.

16.11 Statistical Analysis Plan

A *Statistical Analysis Plan* describing the handling of data issues and the planned statistical analyses in more detail will be prepared by Biostatistics, H. Lundbeck A/S before the study is unblinded.

17 Clinical Study Report and Publications

17.1 Data Ownership

The data collected in this study are the property of Lundbeck.

17.2 Clinical Study Report

For data collected in the Placebo-controlled Period a *Clinical Study Report* will be prepared by Regulatory Medical Writing, H. Lundbeck A/S. Upon completion of the study, an addendum to the *Clinical Study Report*, including the results from the Extension Period, will be produced.

17.3 Summary of Clinical Study Results

Upon completion of the study and when the study results are available, the patient has the right to be informed by the investigator about the overall study results.

17.4 **Publications**

The results of this study will be submitted for publication.

Lundbeck will submit results information:

- to ClinicalTrials.gov
- to EudraCT

The primary publication based on this study must be published before any secondary publications. Authors of the primary publication must fulfil the criteria defined by the International Committee of Medical Journal Editors (ICMJE).⁵⁰

18 Indemnity and Insurance

In the event of study-related injuries or deaths, insurance for the patients and indemnity of the investigators and those of their employees, servants, or agents whose participation in this study has been documented are provided. Insurance and liability will be in accordance with applicable laws and *Good Clinical Practice*.

19 Finance

19.1 Site Agreements

The financial agreements with each site are addressed in one or more documents. Both parties must sign the agreements before each site is initiated.

19.2 Financial Disclosure

All the investigators, including sub-investigators, and raters participating in the study must complete a *Financial Disclosure Form*.

Appendix II Recent and Concomitant Medication Disallowed or Allowed with Restrictions

Recent and Concomitant Medication: Disallowed or Allowed with Restrictions

In the table below, recent and concomitant medications that are disallowed or allowed with restrictions with respect to their use prior to or during the study are listed.

Drug Class	Details
Any investigational drug	Do not use within 30 days or 5 plasma half-lives (whichever is longer) prior to the Screening Visit.
Anticonvulsants	See restrictions in use under anti-migraine agents . Other medication in the same class is allowed if prescribed for non-migraine indications.
Antihypertensives	See restrictions in use under anti-migraine agents . Other medication in the same class is allowed if prescribed for non-migraine indications.
Anti-impotence agents	Allowed if the dose has been stable for at least 12 weeks prior to the Screening Visit.
Anti-inflammatory agents	Allowed if prescribed for non-migraine indications, for example, low dose NSAIDs (acetylsalicylic acid) for cardiovascular disease prevention.
Antimigraine agents	 Acute treatment of migraine (prescription or over-the-counter medication recommended by a healthcare professional) is allowed provided the dose has been stable for at least 12 weeks prior to the Screening Visit. Do not use preventive migraine treatments <1week prior to the Screening Visit and during the study. This includes daily use of: beta-blockers: propranolol, metoprolol anticonvulsants: topiramate, valproate or divalproex tricyclics: amytriptyline calcium channel blocker: flunarizine angiotensin II receptor antagonist: candesartan medication locally approved for prevention of migraine Other medications in the same classes above but not included in this list are allowed. Do not use oral anti-CGRPs for acute treatment <4 weeks prior to the Screening Visit and during the study. Do not use eptinezumab or other monoclonal antibody targeting the CGRP pathway <24 weeks prior to the Screening Visit and during the study. Do not use CNS- and migraine-related devices (neuromodulation, neurostimulation) or injectable therapy (trigger point injections, extracranial nerve blocks, or facet joint injections) <8 weeks prior to the Screening Visit and during the study. Do not use botulinum toxin for migraine or any other medical/cosmetic reason in the head and/or neck region <16 weeks prior to the Screening Visit and during the study.

Drug Class	Details
Hormones	Hormonal therapy (for example, contraceptives, hormone replacement therapy) is allowed provided the dose has been stable for at least 12 weeks prior to the Screening Visit.
Other interventions and devices	See restrictions for CNS- and migraine-related devices under anti- migraine agents . Non-pharmacological interventions (including CBT) are allowed provided the use has been stable for at least 12 weeks prior to the Screening Visit.
Sedatives/hypnotics	 Limited use of the following is allowed provided a stable regimen (<4 days per month) has been maintained for at least 12 weeks prior to the Screening visit. These agents may be prescribed when considered medically indicated by the investigator during the study (including the screening period) providing its use does not exceed 4 days per month: barbiturates (including Fiorinal[®], Fioricet[®], or any other combination containing butalbital). prescription opiates (including single-ingredient or combination medications containing opiates, opioids, tramadol, or tapentadol).
Vaccinations	 COVID-19 vaccinations are allowed during the study with the following guidance: COVID -19 vaccination should not be given within ±3 days of the IMP administration. If the patient has recently received a COVID-19 vaccine, the investigator should judge if the patient can be administered the IMP infusion at the scheduled visit based upon the patient's individual response to the COVID-19 vaccine. Other vaccination are allowed.

DMC	Data Monitoring Committee
EM	episodic migraine
EQ-5D-5L	Euroqol 5 Dimensions
FAS	full-analysis set
FAS_LT	full-analysis-long-term set
HCRU	health care resource utilization
HIT-6	headache impact test
IMP	investigational medicinal product
MAR	missing at random
MBS	most bothersome symptom
MedDRA	Medical Dictionary for Regulatory Activities
MHDs	monthly headache days
ML	maximum likelihood
MMDs	monthly migraine days
MMRM	mixed model for repeated measurements
MNAR	missing not at random
MOH	medication overuse headache
MSQ v2.1	Migraine-Specific Quality of Life Questionnaire Version 2.1
PCS	potentially clinically significant
REML	restricted maximum likelihood
SAE	serious adverse event
$\mathrm{SAS}^{{}_{\mathbb{R}}}$	statistical software package from the SAS® Institute
SD	standard deviation
SE	standard error
SOC	system organ class
TEAE	treatment-emergent adverse event
WPAI:M	Work Productivity and Activity Impairment: Migraine

1 Objectives and Endpoints

The study objectives and endpoints are summarized in Panel 1.

Objectives	Endpoints	
 Primary Objective To evaluate the efficacy of eptinezumab for the prevention of migraine in 	 Primary endpoint: Change from baseline in the number of monthly migraine days (Weeks 1-12) 	
patients with unsuccessful prior preventive treatments	 Key secondary endpoints: Response: patients with 50% reduction from baseline in monthly migraine days (Weeks 1-12) Response: patients with 75% reduction from baseline in monthly migraine days (Weeks 1-12) Change from baseline in the number of monthly migraine days (Weeks 13-24) 	
	 Secondary endpoints: Response: patients with 50% reduction from baseline in monthly migraine days (Weeks 13-24) Response: patients with 75% reduction from baseline in monthly migraine days (Weeks 13-24) Response: patients with 100% reduction from baseline in monthly migraine days (Weeks 1-12) Response: patients with 50% reduction from baseline in monthly headache days (Weeks 1-12) Response: patients with 75% reduction from baseline in monthly headache days (Weeks 1-12) Response: patients with 75% reduction from baseline in monthly headache days (Weeks 1-12) Response: patients with 100% reduction from baseline in monthly headache days (Weeks 1-12) Change from baseline in the number of monthly headache days (Weeks 1-12) Change from baseline in percentage of migraines/headaches with severe pain intensity (Weeks 1-12) Change from baseline in the number of monthly days with use of acute migraine medication (Weeks 13-24) Change from baseline in the number of monthly days with use of acute migraine medication (Weeks 13-24) Change from baseline in the number of monthly migraine days with use of acute medication (Weeks 13-24) Change from baseline in the number of monthly migraine days with use of acute medication (Weeks 13-24) Change from baseline in number of monthly migraine days with use of acute medication (Weeks 13-24) Change from baseline in number of monthly migraine days with use of acute medication (Weeks 13-24) Change from baseline in number of monthly migraine days with use of acute medication (Weeks 13-24) Change from baseline in number of monthly migraine days with use of acute medication (Weeks 13-24) Change from baseline in number of monthly migraine days with use of acute medication (Weeks 13-24) PGIC score at Week 24 Change from baseline in the number of monthly migraine days in patients with Medication Overuse Headac	

Panel 1 Objectives and Endpoints

Objectives	Endpoints
	 Exploratory endpoints: Change from baseline in the number of monthly headache episodes for each 12-week period Change from baseline in the number of monthly migraine attacks for each 12-week period
 Secondary Objectives To evaluate the health-related quality of life and work productivity impact of optimory make 	 Key secondary endpoints: Change from baseline to Week 12 in the Headache Impact Test (HIT-6) score
eptinezumab	 Secondary endpoints: Change from baseline to Week 24 in the HIT-6 score Change from baseline to Week 12 in the Migraine-Specific Quality of Life (MSQ v2.1) sub-scores (Role Function-Restrictive, Role Function-Preventive, Emotional Function) Change from baseline to Week 12 in the Health-Related Quality of Life (EQ-5D-5L) Visual Analogue Scale (VAS) score Health Care Resources Utilization (HCRU) at Week 12 Change from baseline to Week 24 in the MSQ v2.1 sub-scores Change from baseline to Week 24 in the EQ-5D-5L VAS score HCRU at Week 24 Change from baseline to Week 12 in the Work Productivity and Activity Impairment questionnaire (WPAI) sub-scores (Absenteeism, Presenteeism, Work productivity loss, Activity impairment) Change from baseline to Week 24 in the WPAI sub-scores Response: Patients with a 5-point reduction from baseline to Week 24 in HIT-6 score
• To evaluate the effect of long- term treatment with eptinezumab	 Secondary endpoints: Change from baseline in the number of monthly migraine days (Weeks 25-36, 37-48, 49-60, 61-72) Response: patients with 50% reduction from baseline in monthly migraine days (Weeks 25-36, 37-48, 49-60, 61-72) Response: patients with 75% reduction from baseline in monthly migraine days (Weeks 25-36, 37-48, 49-60, 61-72) Change from baseline in the HIT-6 score (at Weeks 36, 48, 60, and 72)
	 Exploratory endpoints: Response: patients with 100% reduction from baseline in monthly migraine days Response: patients with 50% reduction from baseline in monthly headache days Response: patients with 75% reduction from baseline in monthly headache days Response: patients with 100% reduction from baseline in monthly headache days Response: patients with 100% reduction from baseline in monthly headache days Response: patients with 100% reduction from baseline in monthly headache days Change from baseline in percentage of migraines/headaches with severe pain intensity

Objectives	Endpoints
	 Change from baseline in the number of monthly days with use of acute migraine medication Change from baseline in the number of monthly migraine days with use of acute migraine medication PGIC score Change from baseline in the number of monthly migraine days in patients with MOH MBS score Change from baseline in monthly number of Migraine attacks for each 12-week period Change from baseline in monthly number of Headache episodes for each 12-week period Change from baseline in the MSQ v2.1 sub-scores Change from baseline in the EQ-5D-5L VAS score HCRU Change from baseline in the WPAI sub-scores
 Safety Objective To evaluate the safety and tolerability of eptinezumab To evaluate the long-term safety and tolerability of eptinezumab 	 Safety Endpoints Adverse events Absolute values and changes from baseline in clinical safety laboratory test values, vital signs, weight, and ECG parameter values Potentially clinically significant clinical safety laboratory test values, vital signs, weight changes, and ECG parameter values Development of specific anti-eptinezumab antibodies (ADA) including neutralizing antibodies (NAbs) Columbia-Suicide Severity Rating Scale (C-SSRS) score

2 Study Design

This is an interventional, multi-national, multi-site, randomized, double-blind, placebocontrolled Phase IIIb study designed to demonstrate efficacy and safety of eptinezumab for migraine prevention in patients with unsuccessful prior preventive treatments. The placebocontrolled period will be followed by an extension period where all patients will receive active treatment to assess the long-term safety, tolerability and effect of eptinezumab.

The target population for this study is defined as patients with chronic migraine (CM) or episodic migraine (EM), as outlined in the IHS ICHD-3 guidelines¹ with documented evidence of migraine occurring on \geq 4 days per month prior to screening as confirmed via prospectively collected information in the eDiary during the Screening Period, and with documented evidence of failure to 2-4 different preventive migraine medications in the past 10 years. The aim is that approximately 40% of the randomized patients are patients with EM.

It is planned that 840 patients will be randomly allocated to one of three treatment groups: eptinezumab 300 mg, eptinezumab 100 mg, or placebo, in a ratio of 1:1:1.

Randomization will be stratified by country and monthly headache days (MHDs) at baseline (\leq 14 MHDs/>14 MHDs).

The patient will receive IMP starting from the Baseline Visit to follow a dosing schedule with IV infusions every 12 weeks with either eptinezumab or placebo over 30 minutes (+15).

At Visit 8 patients will enter the Extension Period. Patients who were assigned to placebo in the Placebo-controlled Period will be randomly allocated to one of two treatment groups: eptinezumab 300 mg or eptinezumab 100 mg with a ratio of 1:1. Patients assigned to eptinezumab 300 mg or eptinezumab 100 mg in the Placebo-controlled Period will continue on their original assignments.

An overview of the study is presented in Panel 2 and the scheduled study procedures and assessments are summarized in Appendix II. See also the *Clinical Study Protocol* for further details on the study design.

Panel 2 Study Design

For patients who withdraw, except for those who withdraw their consent, a Withdrawal Visit will be scheduled 12 weeks after the last dose of IMP. The withdrawal visit will include Safety Follow-up evaluations and will therefore also serve as a Safety Follow-up Visit.

For patients who withdraw prior to Week 24 the Withdrawal Visit will allow for eDiary closeout and for a final assessment of scales not based on the eDiary. Patients are expected to complete their eDiary until this Withdrawal Visit unless the patient withdraws consent.

2.1 Clinical Study Report

The data collected in the Placebo-controlled Period will be used for generating the output to be included in the *Clinical Study Report* (CSR). Upon completion of the study, an addendum to the *Clinical Study Report*, including the results from the Extension Period, will be produced.

This means that all tables, listings, and figures that are related to the Extension Period or cover the full study period will be prepared after the *Clinical Study Report* for the study is final. This *Statistical Analysis Plan* describes both the output that will be prepared for the *Clinical Study Report* and for the addendum.

Throughout this document, the term *CSR* will be used to refer to the *Clinical Study Report* including the output from the Placebo-controlled Period and the term *addendum to CSR* will be used to refer to the addendum that includes the results from the Extension Period.

3 COVID-19

For this study, all patients are considered to have been enrolled after the beginning of the COVID-19 outbreak.

The following information is collected with regards to COVID-19:

- Whether a visit was done remotely due to COVID-19 including which assessments were/were not performed
- If a visit was not done, whether it was not done due to COVID-19
- Whether patients withdrew due to the COVID-19 situation
- Whether patients got diagnosed with COVID-19

Specific output addressing the impact of COVID-19 for this trial is specified in Sections 7.1 and 7.2.

4 **Definitions**

4.1 Definition of Periods

The study consists of the following periods:

- *Screening Period* (28-30 days): Starts at the Screening Visit and continues up to start of Visit 2 IMP infusion
- *Placebo-Controlled Period*: Starts at start of Visit 2 IMP infusion and continues up to start of Visit 8 IMP infusion
- *Extension Period*: Starts at start of Visit 8 IMP infusion and continues up to and including Visit 20

4.2 Definition of Baseline

For migraine and headache endpoints, the baseline value will be based upon the data recorded in the headache eDiary during the first 28 days following screening.

For other endpoints, the baseline assessment will be the latest available valid measurement taken prior to the administration of IMP.

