The two prior eptinezumab Phase III studies, PROMISE-1 performed in an EM population and PROMISE-2 performed in a CM population, had the following effect sizes for the primary endpoint when compared to placebo (standard deviations):

- EM: 100 mg 0.69 (3.1), 300 mg: 1.11 (3.1)
- CM: 100 mg 2.03 (5.8), 300 mg 2.60 (5.8)

The power was determined by simulating the testing strategy (10000 simulations) assuming normal distributions with similar mean and SD for continuous endpoints and similar success rates as the response variables in the Phase III studies for the corresponding population (EM or CM) without assuming the variables to be correlated. With 280 patients per treatment group, assuming that 40% of the patients will be from the EM population and 60% from the CM population, and that 2% of the patients do not have a post-baseline assessment of the primary endpoint, simulations show that the power for the test of the primary endpoint is approximately 94% for the comparison of 100 mg to placebo and 99% power for the comparison of 300 mg to placebo. The individual key secondary endpoints had a power of at least 68% for showing an effect, with a combined power of 58% for seeing an effect for all primary and key secondary endpoints and both doses in the testing strategy.

Panel 1 Study Design

The study consists of a Screening Period and a Placebo-controlled Period. IMP (eptinezumab 100 mg, eptinezumab 300 mg, or Placebo) is administered by intravenous infusion every 12 weeks, starting at the Baseline Visit. Patients completing the 24-week Placebo-controlled Period will enter an Extension Period where all patients will receive eptinezumab once every 12 weeks.

																					 ,
Visit Name		Baseline^e + IMP	Phone Contact ^k	Phone Contact ^k	Primary Outcome + IMP	Phone Contact ^k	Phone Contact ^k	IMP	Phone Contact ^k	Phone Contact ^k	IMP	Phone Contact ^k	Phone Contact ^k	IMP	Phone Contact ^k	Phone Contact ^k	IMP	Phone Contact ^k	Phone Contact ^k	Completion	Withdrawal ^v
	Placebo-controlled Period									Extension Period											
Visit Number	1	2	3	4	5	6	7	8	9	10	11	12	13	14	15	16	17	18	19	20	
End of Week ^a	-4	0	4	8	12	16	20	24	28	32	36	40	44	48	52	56	60	64	68	72	
Visit Window ^b (days relative to nominal visit)	-2		-2	±2	±2	±2	±2	±2	±2	±2	±2	±2	±2	±2	±2	±2	±2	±2	±2	+2	+2
Screening and Baselin	e Pr	oceo	lure	es an	d A	sses	sme	nts													
Signed informed consents	\checkmark																				

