13.2 General Methodology for Other Safety Data

Unless otherwise specified, tables, graphs, and listings will be based on the APTS for the Placebo-controlled Period and APTS_LT for the Extension Period.

All tables and graphs will be presented by treatment group for the Placebo-controlled Period and by treatment sequence group for the Extension Period.

The denominators for the summaries of a given variable will be based on the number of patients with non-missing values at a given visit or during the assessment period.

Descriptive statistics for the safety variables, both absolute values and changes from baseline, will be presented by visit, separately for each period.

The number and percentage of patients with at least one PCS value at any post-baseline assessment time point will be summarized by variable, separately for each period. All available assessments in each period will be included in the evaluation of PCS values.

For patients with post-baseline PCS values in the Placebo-controlled Period, listings will be provided including all the values for those patients for the variable prior to entering the Extension Period, with flagging of PCS values and out-of-reference-range values for inclusion in the *CSR*.

For patients with PCS values occurring after start of V8 IMP infusion, similar listings will be provided including all the values for those patients for the variable for inclusion in the *addendum to CSR*.

For inclusion in the *CSR*, all the adverse events occurring before entering the Extension Period in patients with post-baseline PCS values in the Placebo-controlled Period will be listed by treatment group and patient screening number; the listing will include the PCS value, the assessment date, the change from baseline in PCS value, the preferred term for the adverse event, and start date and stop date of the adverse event. The PCS values and adverse events will be listed in chronological order according to assessment date and the start date of the adverse event.

Similar listings will be provided for patients with PCS values occurring after start of V8 IMP infusion, including all the adverse events for the patients, for inclusion in the *addendum to CSR*.

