19.2.2 Safety Variables

Laboratory Tests and ECG

Assessments of laboratory tests and ECGs at unscheduled visits and withdrawal visits will be assigned to a nominal visit in the Placebo-controlled Period according to the visit windowing specified in Panel 10 for patients in the APTS. Assessments for patients not receiving any infusions of IMP will be assigned to Visit 2 (Baseline). For patients receiving an infusion of

IMP in the Extension Period, assessments of laboratory tests and ECGs at unscheduled visits and withdrawal visits will be assigned to a nominal visit in the Extension Period according to the visit windowing specified in Panel 11.

Panel 10 Visit Windows for Placebo-Controlled Period – Laboratory tests, ECG

Nominal Visit Number	Nominal Visit Week	Nominal Visit Day	Time Window
V1 (Screening Visit)	-4	-28	NA
V2 (Baseline Visit)	0	0	NA
V5	12	84	After start of first IMP infusion to day 126
V8	24	168	Day 127 to start of Visit 8 IMP infusion

Panel 11 Visit Windows for Extension Period – Laboratory tests, ECG

Nominal Visit Number	Nominal Visit Week	Nominal Visit Day	Nominal Visit Day Relative to Visit 8 IMP Infusion	Time Window Relative to Visit 8 IMP Infusion
V11	36	252	84	After start of Visit 8 IMP infusion to day 126
V14	48	336	168	Day 127 to day 210
V17	60	420	252	Day 211 to day 294
V20	72	504	336	> 294

Vital signs will be assessed before and after infusion at nominal visits. For unscheduled or withdrawal visit assessments of vital signs, the values will be assigned a nominal visit according to Panel 12 and Panel 13.

Nominal Visit Number	Nominal Visit Week	Nominal Visit Day	Time Window
V1 (Screening Visit)	-4	-28	NA
V2 (Baseline Visit) pre-dose	0	0	NA
V2 (Baseline Visit) post-dose	0	0	After start of first IMP infusion to day 42
V5 pre-dose	12	84	Day 43 to start of V5 IMP infusion
V5 post-dose	12	84	After start of V5 IMP infusion to day 126
V8 pre-dose	24	168	Day 127 to start of Visit 8 IMP infusion

Panel 12 Visit Windows for Placebo-Controlled Period – Vital Signs

Nominal Visit Number	Nominal Visit Week	Nominal Visit Day	Nominal Visit Day Relative to Visit 8 IMP Infusion	Time Window Relative to Visit 8 IMP Infusion
V8 post-dose	24	168	0	After start of V8 IMP infusion to day 42
V11 pre-dose	36	252	84	Day 43 to start of V11 IMP infusion
V11 post-dose	36	252	84	After start of V11 IMP infusion to day 126
V14 pre-dose	48	336	168	Day 127 to start of V14 IMP infusion
V14 post-dose	48	336	168	After start of V14 IMP infusion to day 210

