S-triglycerides, non- fasting/unknown	TRIG	mmol/L		≥ 5.65
S-triglycerides, fasting	TRIG	mmol/L		\geq 4.2
S-LDL cholesterol, non- fasting/unknown	LDL	mmol/L		≥ 5.3
S-LDL cholesterol, fasting	LDL	mmol/L		\geq 4.9
S-HDL cholesterol, non- fasting/unknown	HDL	mmol/L	≤ 0.8	
S-HDL cholesterol, fasting	HDL	mmol/L	≤ 0.9	
Cardiac/Skeletal/Muscle				
S-creatine kinase (total)	CK	U/L		\geq 400 (women) \geq 750 (men)
S-creatine kinase MB isoenzyme	CKMB	μg/L		$\geq 8.5 \text{ or}$
5	CKMBCK	%		\geq 3.5% of total CK
S-lactate dehydrogenase (total)	LDH	IU/L		≥ 750
S-troponin I	TROPONI	µg/L		≥ 1.5
S-troponin T	TROPONT	μg/L		≥ 0.4
Infection		-		
S-C-reactive protein	CRP	mg/L		≥25
S-globulin (total)	GLOBUL	g/L	≤15	≥ 55

Laboratory Test	CDISC Term	Unit	PCS Low	PCS High
Urine				
Urinary pH	PH		\leq 4	≥ 9

Table 4 PCS Criteria for Vital Signs, Weight/BMI, and Waist Circumference

Variable	CDISC Term	Unit	PCS Low	PCS High
Waist circumference	WSTCIR	Cm	decrease $\geq 7\%$	increase $\geq 7\%$
Weight	WEIGHT	Kg	decrease $\geq 7\%$	increase $\geq 7\%$
Body Mass Index	BMI	kg/m2	decrease $\geq 7\%$	increase $\geq 7\%$
Pulse rate, supine/sitting/unknown	PULSE	beats/min	< 50 and decrease ≥ 15	\geq 120 and increase \geq 15
Diastolic blood pressure, supine/sitting/unknown	DIABP	mmHg	≤ 50 and decrease ≥ 15	\geq 105 and increase \geq 15
Systolic blood pressure, supine/sitting/unknown	SYSBP	mmHg	\leq 90 and decrease \geq 20	\geq 180 and increase \geq 20
Orthostatic systolic blood pressure	OBP	mmHg	≤ -30	
Orthostatic pulse rate	OPR	beats/min		≥ 20
Temperature	TEMP	°C	decrease ≥ 2	\geq 38.3 and increase \geq 2

Increase/decrease is relative to the baseline value.

Table 5PCS Criteria for ECG Parameters

ECG Parameter	CDISC Term	Unit	PCS Low	PCS High
Absolute Time Interval				
PR interval	PRAG	Msec		≥ 260
QRS interval	QRSAG	Msec		≥ 150
QT interval	QTAG	Msec		\geq 500
Derived Time Interval				
Heart rate	EGHRMN	beats/min	< 50 and decrease ≥ 15	\geq 120 and increase \geq 15
QTcB interval	QTCBAG	Msec	< 300	> 500 or increase > 60
QTcF interval	QTCFAG	Msec	< 300	> 500 or increase > 60

Increase/decrease is relative to the baseline value.

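### For placebo patients who switch at Visit 8, Extension Period safety changes and baseline-relative PCS flags are measured from Visit 2 and so include 24 weeks on placebo

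*SAP*

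**What the plan says.** SAP 4.2 has two baseline rules. The rule for the eDiary outcomes reads: "the baseline value will be based upon the data recorded in the headache eDiary during the first 28 days following screening". Everything else, including all safety variables, falls under the second rule: "For other endpoints, the baseline assessment will be the latest available valid measurement taken prior to the administration of IMP".

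The text to Panel 1 of the protocol makes placebo part of IMP: "IMP (eptinezumab 100 mg, eptinezumab 300 mg, or Placebo) is administered by intravenous infusion every 12 weeks, starting at the Baseline Visit". The visit-window panels in SAP 19.2.2 label Visit 2, Week 0, as the Baseline Visit and give Visit 8 no such label.

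The Extension Period (SAP 4.1) "Starts at start of Visit 8 IMP infusion and continues up to and including Visit 20". At that visit (SAP 2), "Patients who were assigned to placebo in the Placebo-controlled Period will be randomly allocated to one of two treatment groups", 300 mg or 100 mg in a 1:1 ratio.

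The baseline then enters the Extension Period outputs in three places:

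- SAP 13.2 presents absolute values and changes from baseline by visit within each period. It also counts PCS values by period: "patients with at least one PCS value at any post-baseline assessment time point will be summarized by variable".
- SAP Appendix V, under Tables 4 and 5: "Increase/decrease is relative to the baseline value".
- SAP 13.5 tabulates QTcF increases of more than 30 and more than 60 msec from baseline for both periods.

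Neither document defines a separate Extension Period baseline. Panels 11 and 13 count days from the Visit 8 infusion, but only to assign assessments to visits.

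**The concern.** A placebo patient is first exposed to eptinezumab at Visit 8. The useful within-patient safety question for that patient in the Extension Period is what changed after Visit 8. The planned summaries answer a different one: what changed since study entry, with the first 24 weeks spent on placebo.

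This matters because long-term safety is a stated objective, the extension has no concurrent placebo group, and the planned 280 placebo patients (fewer after withdrawals) have their first exposure there. SAP 13.2 gives them their own sequence columns, which helps. Within those columns, though, a change that arose on placebo appears as an Extension Period change or PCS event, and a change that arose on drug can be offset by an opposite movement on placebo.

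**Working it through.** The plan states no figure on this point, so there is none to reproduce. The power statement in SAP 16 uses no safety baseline.

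**1. Share of the interval spent on placebo.** With a Visit 2 baseline, the change at week w covers w weeks, of which 24 are on placebo. The share is 24/w. From Visit 8 the interval is w − 24 weeks, all on eptinezumab.

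| Visit (week) | From Visit 2 | From Visit 8 | Placebo share of Visit 2 interval |
|---|---|---|---|
| V11 (36) | 36 wk | 12 wk | 24/36 = 67% |
| V14 (48) | 48 wk | 24 wk | 24/48 = 50% |
| V17 (60) | 60 wk | 36 wk | 24/60 = 40% |
| V20 (72) | 72 wk | 48 wk | 24/72 = 33% |

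**2. Which PCS criteria are exposed (Appendix V).**

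- Table 3, laboratory: absolute limits or multiples of a reference limit. Baseline plays no part in the PCS counts; it enters only the summaries of laboratory change.
- Table 4: weight and BMI (±7%) and temperature decrease (≥2 °C) depend on change alone. Pulse, blood pressure and high temperature need an absolute threshold as well as a change.
- Table 5: a QTcB or QTcF increase >60 msec is sufficient alone. Heart rate also needs an absolute threshold.

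**3. Two constructed patients, weight criterion ≥7%.**

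- 80 kg at Visit 2, 86 kg at Visit 8, 86 kg afterwards. From Visit 2: 86/80 − 1 = +7.5%, PCS at every extension visit. From Visit 8: 0%.
- 80 kg at Visit 2, 76 kg at Visit 8, 82 kg on eptinezumab. From Visit 8: 82/76 − 1 = +7.9%, over the limit. From Visit 2: 82/80 − 1 = +2.5%, not flagged.

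**4. How often, under assumed models.** The documents give no SD for weight change, so the SD of 24-week change is an assumption and no drug effect is included. The table gives the share of switchers with any weight change of ≥7% at Visits 11, 14, 17 or 20, from a simulation of 400,000 patients.

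| Model, 24-week SD | From Visit 2 | From Visit 8 | Flagged from Visit 2 only | Flagged from Visit 8 only |
|---|---|---|---|---|
| Random walk, 2.5% | 14% | 6% | 10% | 2% |
| Random walk, 3% | 24% | 12% | 15% | 4% |
| Random walk, 4% | 43% | 28% | 22% | 7% |
| Random walk, 5% | 58% | 43% | 24% | 10% |
| Independent visits, 3% | 6.6% | 6.6% | 5.5% | 5.5% |
| Independent visits, 4% | 24% | 24% | 15% | 15% |

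The random walk uses independent 12-week steps with SD equal to the 24-week SD divided by √2. Under independent visits, each value varies about a fixed level, with the same SD for the difference between two visits.

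If drift accumulates, the Visit 2 baseline inflates the total. If it does not, the totals agree but the two baselines flag partly different patients.

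**The case against.** The strongest reply is that the plan already lets a reader see most of this. Switchers are not pooled with continuing patients in the safety tables, absolute values are shown by visit, and the Extension Period PCS listings carry all of a flagged patient's values. The 86 kg patient's Visit 8 weight would be visible, and that patient would already be PCS in the Placebo-controlled Period, to which the pre-dose Visit 8 value belongs. Treatment-emergent adverse events are assigned to periods by onset relative to the Visit 8 infusion (SAP 13.1.4), and weight, vital-sign and ECG findings judged clinically significant are recorded as adverse events whatever their PCS status (protocol 9.4.3 to 9.4.5). All of that stands. What remains is that no summary table shows change since first exposure, and that the 80-76-82 kg patient need not appear in any weight PCS listing.

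The second reply concerns size, and it also stands. The random-walk gap is one assumed model, and part of it is only the longer interval, up to 72 weeks against 48. Few patients under that model are already past 7% at Visit 8 (about 2% at SD 3%, 8% at SD 4%), so most flags that appear only from Visit 2 combine change on placebo with change on drug.

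Three stronger readings are tempting and not supported:

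- That the plan attributes placebo drift to eptinezumab. It labels the quantity change from baseline within a placebo-eptinezumab sequence.
- That within-patient change is the only safety evidence in these patients. Adverse events, absolute values and the randomized 24 weeks also bear on it.
- That laboratory PCS counts are distorted. Table 3 does not use baseline.

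**Conclusion.** The gap is real and limited. For the two placebo-eptinezumab sequences, Extension Period safety changes, the PCS criteria that rest on change from baseline and the QTcF increase categories are referenced to a value taken 24 weeks before first exposure. That placebo time makes up two thirds of the interval at Week 36 and one third at Week 72. Misclassification in both directions follows from the definitions and needs no model. Its frequency, and any inflation of totals, rest on an assumed drift pattern and SD, so the simulated percentages are illustrations only.

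The effect is confined to descriptive outputs in the addendum to the study report. No hypothesis test, estimand or power figure changes, and the placebo-controlled safety comparison is untouched. The reading that baseline means Visit 2 rests on the Baseline Visit label and on placebo being IMP. SAP 4.2 does not itself say which administration of IMP is meant.

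**What to change.** In SAP 4.2, insert 'first' before 'administration of IMP' in the rule for the study baseline. Add a second baseline for the placebo-eptinezumab sequences: the last valid value before the start of the Visit 8 infusion. In those sequences, use it for Extension Period safety changes from baseline (13.2), the baseline-relative PCS criteria (Tables 4 and 5) and the QTcF change categories (13.5).

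Keep the Visit 2 display beside it. Replacing Visit 2 would lose change since study entry and leave two of the four sequence columns on a different reference from the other two.

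The cost is one derived flag, a footnote and a few more descriptive outputs in the addendum. No new data are needed: laboratory samples, ECG and vital signs are scheduled before the Visit 8 infusion, and weight is scheduled at the same visit (protocol Panel 2). Some Visit 8 values may be missing where visits were remote or missed, so the rule should fall back on the last earlier valid value and the tables should state how often it did.
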